2.2.2 Secondary Endpoints

Secondary Endpoints:

- 1) Retention, adherence and ability to collect clinical outcomes from participants
- 2) Time to delivery from presentation and gestation at delivery
- 3) Contraction frequency as monitored at presentation and from randomisation to delivery or cessation of regular uterine activity.
- 4) Maternal markers of inflammation including, but not limited to: IL-6, IL-10, IL-13, IL-17, TNFa, IL-1RA, sTNF-RI, sTNF-R2, and HO-1, as well as levels of the soluble IL-6R and the inhibitor spg130 (abbreviated hereafter to 'Inflammatory Profile')
- 5) Fetal measures of inflammation including but not limited to: (cord IL-1, IL-6, IL-8, sIL-6R and sgp130.
- 6) Adverse events (maternal and fetal)
- 7) Time from time first seen in an acute obstetric care setting to administration of trial medication as documented in the participant medical records.
- 8) Compliance with 7 days of blinded treatment
- 9) Acceptability of the trial to those who have participated
- 10) Pharmacokinetic parameters as compared with current published data
- 11) Maternal outcomes:
 - a. Proven maternal infection
 - b. Safety of intervention to mother (self-reported AEs and biochemical monitoring of liver function tests and creatinine kinase).
 - c. Pre-labour ROM
 - d. Duration, location and level of care of hospital stay following presentation with suspected preterm labour AND following delivery.
- 12) Neonatal outcomes:
 - a. Details of in utero transfers including mode of transport required
 - b. Gestational age at delivery, morbidity and mortality, birthweight, duration and location of hospital stay post-delivery and up to 28 days post EDD.
 - c. Safety of intervention

CR007-T01 v4.0 PIPIN Protocol Version 5.0 17/05/2019 Page **14** of **45**

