With an expected death rate of 6%, we consider that a doubling of this rate would be grounds for serious concern, if such deaths were thought to be related or possibly related to study IMP, that will prompt a halt in recruitment pending review by the independent DMC (iDMC), We will randomize around 20 to pravastatin, and assume there is no cross over from placebo to pravastatin (although of course as safety data these will be analysed according to treatment received). If there is 1 death thought to be related to IMP in any the first 10 randomised to pravastatin, or cumulatively 2 deaths in the first 20 randomised to pravastatin, this will trigger a review by the iDMC, and if the iDMC believes that it is plausible that the deaths are related to the IMP, the DMC will advise whether the trial should be stopped, or the circumstances under which the trial should continue.

The two most severe class side effects of statins, that is liver toxicity (defined by jaundice, hepatitis or fulminant hepatic necrosis) and muscular toxicity (rhabdomyolysis), both occur at a frequency of less than 1 < 10,000. Occurrence of these in any participant with reasonable suspicion of causation due to the IMP will prompt review of unblinded data by the DMC.

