4. STUDY POPULATION

4.1 NUMBER OF PARTICIPANTS

We will to recruit 40 participants. Eligible participants are pregnant women presenting in preterm labour at 24+0 to 35+6 weeks gestation. Preterm labour is defined as regular uterine activity with either a positive fetal fibronectin (See Appendix 5) or evidence of cervical change as monitored through cervical length scanning or direct observation of dilation.

We estimate a duration of 2 years with an 18 month recruitment period. Follow up of participants to last Participant last visit will take up to another 6 months.

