4.2 INCLUSION CRITERIA

To be eligible to take part in the PIPIN study, the below inclusion criteria must be met:

- Ability to Give Consent
- Gestation ≥24+0 and ≤ 35+6 weeks (based on dating scan obtained at ≤ 16 weeks gestation)
- Singleton pregnancy
- Aged 16 years or above
- Not previously recruited to this study in this pregnancy
- Intact membranes
- A positive fetal fibronectin test (See Appendix 5) OR a short cervical length (≤ 15mm) on ultrasound examination OR cervical dilation ≥ 3cm and less than fully dilated
- Uterine activity defined as ≥ 1 palpable contraction over 20 minutes of CTG monitoring.

CR007-T01 v4.0 PIPIN Protocol Version 5.0 17/05/2019 Page **17** of **45**

- No major congenital anomalies evident on the 20 week anomaly scan, or any further anomaly scans performed subsequently. If an anomaly is present, this should be classified as per ICD-10 codes and minor anomalies discussed for inclusion on a case by case approach involving the clinical team, the PI and the participant.
- Not demonstrating any of the exclusion criteria as detailed below

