5.5 RANDOMISATION

5.5.1 Randomisation Procedures

Participants will be randomised to active or placebo in a 1:1 ratio. Randomisation block size will use permuted blocks of size 2, 4, and 6, randomly sorted, and spliced with occasional randomly inserted simple runs of random length to aid unpredictability. Randomisation codes will be provided to ISG by ECTU, and packs dispensed in a sequential fashion from these. Details of the study pack number allocated will be recorded in the Participant's notes, on the medication record as well as in the drug accountability log in the treatment room of labour ward.

This trial will be double blinded. Randomisation codes will be held by both ECTU and the local Pharmacy department.

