10.2 PROPOSED ANALYSES

Measures to be reported:

Primary outcome data

1. Trial uptake: eligible participants as compared with recruitment.

Secondary Outcome Data

- 1. Routine participant demographics including past medical history and drug history
- Any additional treatments received during inpatient stay (including magnesium sulphate, antibiotics, syntocinon / other methods of induction/augmentation and steroids)
- 3. Retention, adherence and ability to collect clinical outcomes from participants
- 4. Time from presentation with threatened preterm labour to delivery of first dose of IMP.
- 5. Time from presentation to acute care and assessment services with suspected preterm delivery to delivery itself, as well as gestation at delivery
- 6. Contraction frequency during treatment course, from presentation to delivery or cessation of regular uterine activity.
- 7. Bloods: Liver function tests, creatinine kinase levels (side effects), maternal and cord inflammatory profile (see 2.2.2 for details of measures within the inflammatory profile).
- 8. Compliance with treatment
- 9. Adverse events
- 10. Acceptability of the trial following completion of the protocol
- 11. Other clinical outcomes
 - a. Maternal outcomes:
 - i. Proven maternal infection (See Appendix 4: Glossary of Terms for definition)

CR007-T01 v4.0 PIPIN Protocol Version 5.0 17/05/2019 Page **29** of **45**

- ii. Safety of intervention to mother (self-reported AEs and biochemical monitoring of liver function tests and creatinine kinase).
- iii. Pre-labour ROM
- iv. Duration, location and level of care of hospital stay following presentation with suspected preterm labour AND following delivery.
- b. Neonatal morbidity and mortality, safety of intervention, gestational age at delivery, birthweight, duration, location and level of care required following delivery. If in utero transfer occur, cause of method of transport used.
- 12. Pharmacokinetics of pravastatin

Participant uptake the study will involve a direct analysis of eligible participants presenting to acute care and assessment services compared with recruitment. Secondary outcomes 1 and 2 will be used to perform subgroup analysis and identify potential confounders between treatment and placebo arms. Outcomes 3 - 11 will be used to directly compare treatment and placebo arms of the trial, and inform design for a large scale trial in the future.

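### Section 10.2 compares gestation at delivery and birthweight directly between arms without fixing entry gestation as a covariate, which costs precision at about 20 women per arm

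*Protocol*

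**What the plan says.** - **Outcome.** Section 2.2.2 lists "Time to delivery from presentation and gestation at delivery" as one secondary endpoint. Section 10.2 repeats the pair as outcome 5, and names gestational age at delivery again, with birthweight, among the neonatal outcomes under item 11.
- **Entry.** Section 4.2 admits women at "Gestation ≥24+0 and ≤ 35+6 weeks".
- **Size and allocation.** Section 4.1: "We will to recruit 40 participants". Section 3, under the stopping rules: "We will randomize around 20 to pravastatin". Section 5.5.1: "Participants will be randomised to active or placebo in a 1:1 ratio" and "Randomisation block size will use permuted blocks of size 2, 4, and 6, randomly sorted", with occasional simple random runs. No stratification or minimisation by gestation is stated.
- **Comparison.** Section 10.2: "Outcomes 3 - 11 will be used to directly compare treatment and placebo arms of the trial".
- **Covariates.** Section 10.2: "Secondary outcomes 1 and 2 will be used to perform subgroup analysis and identify potential confounders between treatment and placebo arms". Outcome 1 is demographics with medical and drug history. Outcome 2 is treatment given during the inpatient stay, for example magnesium sulphate, steroids and augmentation of labour.
- **Data at hand.** Section 7.2 counts gestational age among the screening demographics, and its schedule table records it at screening and at delivery.
- **Deferral.** Section 10.2 leaves further detail to a SAP to be signed off before unblinding.

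**The concern.** Entry gestation is a floor for gestation at delivery, and the floor varies by almost 12 weeks between women. In two groups of about 20 its mean can easily differ by a week or more by chance. An unadjusted difference in gestation at delivery carries that gap with it, and so does birthweight to the extent that it follows gestation.

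The route that 10.2 gives for dealing with imbalance has two weaknesses.

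1. It looks for confounders between randomised arms. Read literally, covariates could be chosen because the arms happen to differ on them, when they should be fixed in advance because they predict outcome.
2. Half of the candidate list (outcome 2) is care that can be given after randomisation and can depend on how labour progresses. Adjusting for it could remove or distort part of a treatment effect.

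The baseline variable tied most directly to the outcome is not singled out.

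At stake is how informative these comparisons are. Section 10.2 uses outcomes 3 to 11 to inform the design of a large trial. Section 10.1 names time to delivery among the data that decide whether such a trial is warranted.

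**Working it through.** The protocol gives no SD, effect size or power for these outcomes, so there is no stated figure to reproduce. The SDs, the 1-week effect and the latencies (time from entry to delivery) below are assumptions.

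**1. Chance imbalance at entry**

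Inputs from the protocol: 20 women per arm; window 24+0 to 35+6, which is 83 days or 11.86 weeks from end to end.

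Upper assumption for the entry SD, entries spread evenly: 11.86/√12 = 3.42 weeks. Counting the window as 12 whole weeks gives 12/√12 = 3.46. Lower values apply if entries cluster.

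SE of the difference in mean entry gestation = SD × √(1/20 + 1/20) = SD × 0.316; 95% range = ±1.96 × SE.

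| Assumed entry SD (weeks) | SE | 95% range | P(gap > 1 week) |
|---|---|---|---|
| 2.0 | 0.63 | ±1.24 | 11% |
| 2.5 | 0.79 | ±1.55 | 21% |
| 3.0 | 0.95 | ±1.86 | 29% |
| 3.42 | 1.08 | ±2.12 | about 36% |
| 3.46 | 1.10 | ±2.15 | 36% |

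A gap of more than 1 week is therefore realistic. A gap of more than 2 weeks has probability 0.2% at SD 2.0 and 7% at SD 3.46.

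**2. Does this hide any effect?**

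Suppose, optimistically, that gestation at delivery had no more spread than gestation at entry. Unadjusted two-sided 5% power at 20 per arm would be:

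| True effect | Entry SD 3.46 | Entry SD 2.0 |
|---|---|---|
| 1 week | 15% | 35% |
| 2 weeks | 45% | 89% |
| 3 weeks | 78% | 99.7% |

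An effect near 1 week can be lost. One of 3 weeks would usually show.

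**3. What adjustment buys**

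Simulation with 20 per arm and 4,000 runs per scenario: unadjusted t-test against a linear model with entry gestation as covariate, for a 1-week shift in delivery. Entry was either uniform over the window or skewed to later gestations.

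| Assumed time to delivery | Correlation of entry and delivery gestation | SD of estimated difference (no effect), unadjusted → adjusted | Power for 1 week, unadjusted → adjusted |
|---|---|---|---|
| Median 1 week, uniform entry | 0.93 | 1.16 → 0.44 | 14% → 64% |
| Median 1 week, late-skewed entry | 0.89 | 0.92 → 0.42 | 19% → 65% |
| Median 3 weeks, uniform entry | 0.71 | 1.30 → 0.93 | 11% → 18% |
| Median 3 weeks, late-skewed entry | 0.64 | 1.01 → 0.78 | 16% → 23% |
| Half of women reach near term (four scenarios) | 0.32 to 0.36 | e.g. 1.47 → 1.41 | 10–17% → 11–18% |

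Check: adjustment should shrink the SD by about √(1 − r²). For r = 0.93 that is 0.37, and 1.16 × 0.37 = 0.43, against 0.44 simulated. For r = 0.36 it is 0.93, and 1.47 × 0.93 = 1.37, against 1.41.

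With no true effect, the rejection rate was 4.7% to 5.7% unadjusted and 4.8% to 5.6% adjusted. Neither analysis is biased; they differ in precision.

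**4. Time to delivery**

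Gestation at delivery = entry gestation + time to delivery, if both are taken from the same moment. An unadjusted comparison of time to delivery therefore subtracts entry gestation with a slope of exactly 1. That works if latency does not depend on entry gestation. Taking the due date as 40+0 by convention, about 16 weeks remain to it at 24+0 and about 4 at 35+6, so long latencies are possible only for early entrants. A pre-specified covariate lets the data set the slope.

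**The case against.** **Covariates belong to the SAP.** The SAP is not shown, is to be signed off before unblinding, and may name entry gestation. A missing covariate list would be no finding. What stands is that 10.2 is not silent: it prescribes a search for confounders between arms and names inpatient treatments as candidates. A SAP that followed it would inherit both features.

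**Covariates need not be picked after seeing the arms.** Sign-off before unblinding allows them to be fixed blind. This is fair. The wording permits selection on observed differences without requiring it.

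**Entry gestation is available to the analysis.** A reader might infer from 10.2 that it goes unused. Section 7.2 does not support that, because it counts gestational age among the screening demographics, so outcome 1 may include it. The supported statement is that it is not pre-specified.

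**A direct comparison need not be unadjusted.** A reader might take the phrase to rule out a model. It does not; no test or estimator is named.

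**Time to delivery already removes the offset.** It does so arithmetically, and it is the item of this pair that 10.1 names for deciding on a large trial. That lowers the stakes for gestation at delivery. It does not make time to delivery independent of entry gestation, and birthweight has no such companion measure.

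**Conclusion.** The point holds as one of precision and pre-specification. Section 10.2 sets up a direct comparison of gestation at delivery and birthweight in about 20 women per arm. It does not fix entry gestation as a covariate, and it describes a weaker route to covariates. Under assumed entry SDs of 2.0 to 3.4 weeks, chance can leave the arms ±1.2 to ±2.1 weeks apart at entry, enough to exceed an effect of about 1 week.

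Three stronger readings are not supported:

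- **Imbalance would swamp any effect.** The protocol states no effect size, and a 3-week effect would usually be visible under the optimistic spread in step 2.
- **The observed difference would mostly reflect who enrolled early or late.** That depends on latency, which the protocol does not give. At a correlation of 0.35, entry gestation explains 0.35² = 12% of the variance.
- **The comparison is biased.** Type I error stays near 5% with or without adjustment.

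Priority is minor to moderate. These are secondary outcomes in a 40-woman feasibility trial whose primary outcome is recruitment and which makes no power claim. The change is worth making because it is nearly free and, in the scenarios examined, did no material harm.

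**What to change.** In section 10.2, and then in the SAP, state that:

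- gestation at delivery, birthweight and time to delivery are compared between arms with adjustment for gestation at randomisation, as a continuous covariate fixed in advance;
- covariates are not chosen from observed differences between arms, and treatments given after randomisation are reported by arm but not used as adjustment variables.

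The sentence on identifying confounders from outcomes 1 and 2 should be replaced or limited accordingly. Unadjusted summaries can still be shown beside the adjusted estimates.

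Cost: about two sentences of text and one degree of freedom per model (with 40 women, 38 residual degrees of freedom become 37). No new data are needed, since gestational age is already recorded at screening. Randomisation need not change.

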Compliance (number of tablets taken) will be collected from the participants' medical records and at the day 7 trial visit (from the participant's diary) and the returned medication bottles. Serum pravastatin levels will also be taken to evaluate compliance.

Timing from presentation to first dose administered

Timing of presentation to first treatment dose administered will be collected from the participants' medical records.

Delivery, post-natal and neonatal outcomes

At the time of delivery, secondary outcomes of gestational age at delivery, markers of fetal and maternal inflammation and pravastatin levels will be collected (via medical records and maternal and cord blood samples).

Maternal and neonatal outcomes will be monitored and information extracted from the participants medical records until EDD + 28 days.

Acceptability of the Trial

This will be collected at two points:

- 1) Percentage uptake of eligible participants to the trial
- 2) At or near 28 days post EDD, participants will be contacted using their preferred method of contact, thanked for their involvement and asked for feedback.

Stopping Rules

We have set the following safety rules for PIPIN based on maternal and neonatal deaths that are possibly or definitely related to IMP. We have based these rules on the expected frequency of maternal and neonatal deaths in the population.

CR007-T01 v4.0 PIPIN Protocol Version 5.0 17/05/2019 Page **16** of **45**

We do not anticipate that there will be any maternal deaths (maternal death rate in the UK is 8.5 per 100,000). So in n=40 women we would not expect any deaths – we would need to recruit almost 12,000 women to expect 1 death.

We anticipate that the death rate of babies in the PIPIN population will be at least 6% (based on the Oracle study, which also recruited women in preterm labour (Kenyon et al. 2001). The Oracle study recruited women suspected clinically to be in preterm labour; in PIPIN we will recruit women in whom a "test" has additionally confirmed the onset of preterm labour, hence preterm birth (with associated neonatal death) is more likely to occur in PIPIN).

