Participants will be contacted by their preferred method of contact and acceptability of the trial discussed with them.

CR007-T01 v4.0 PIPIN Protocol Version 5.0 17/05/2019 Page **25** of **45**

The table below summarises this information.

Assessment or outcome	Screening	Randomisation	Day 1	Daily until discharge	Day 7	At Delivery	28 days post EDD
Clinical Measures				J			
Blood pressure	Х						
Fetal Fibronectin / Cervical Length	Х						
/ cervical dilation (one only required)	x						
Contraction Frequency	Х		Х	Х	Х		
Biochemical Measures							
Urea		Х	Х				
Serum creatinine		Х	Х				
Albumin		Х	Х		Х		
Liver transaminases		Х	Х		Х		Х
Inflammatory Profile		Х	Х	Х	Х	Х	
Haematological Measures							
Haemoglobin		Х					
Maternal							
Maternal mortality/ morbidity		Х	Х	Х	Х	Х	Х
Serious adverse events or reactions		Х	х	x	х	x	x
Routine CTG		Х	Х	Х	Х		
Serum Pravastatin			Х	Х	Х	Х	
Fetal & Neonatal Measures							
Gestational age (from EDD by ≤ 16 week scan)	х					x	
Cord inflammatory profile						Х	
Cord pravastatin levels						Х	
Apgar score at 1,5,10 minutes						Х	
Congenital anomalies	Х					Х	
Neonatal mortality/ morbidity						Х	Х
Length of maternal and perinatal hospital stay and location						х	X

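### Section 10.2 looks for confounders of the between-arm comparison in a list that omits the entry criterion met, and randomisation is not stratified by it; fixing adjustment for it in advance may sharpen the time-to-delivery estimate

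*Protocol*

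**What the plan says.** - **Entry.** Section 4.2 admits women with "A positive fetal fibronectin test (See Appendix 5) OR a short cervical length (≤ 15mm) on ultrasound examination OR cervical dilation ≥ 3cm", the last running up to just short of full dilation. Gestation may be anything from 24+0 to 35+6 weeks. The schedule in section 7.2 lists fibronectin, cervical length and "cervical dilation (one only required"), so a woman need not have all three measured.
- **Allocation.** Section 4.1 plans 40 participants. Under section 5.5.1, "Participants will be randomised to active or placebo in a 1:1 ratio", and "Randomisation block size will use permuted blocks of size 2, 4, and 6, randomly sorted", with occasional simple runs inserted. No stratification or minimisation factor is named.
- **Analysis.** In section 10.2, "Outcomes 3 - 11 will be used to directly compare treatment and placebo arms of the trial". Time from presentation to delivery is item 5. Items 1 and 2 serve for subgroup analysis and for finding confounders between the arms. Item 1 is demographics with medical and drug history. Item 2 is additional treatment during the inpatient stay: magnesium sulphate, antibiotics, steroids, induction or augmentation. Entry criterion is in neither item.
- **Use.** Section 10.1 declines a power calculation and makes recruitment rate the primary outcome. Time to delivery is one of the further inputs to the decision on a large trial.
- **Deferral.** Section 10.2 ends by referring further detail to an SAP to be signed off before unblinding.

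**The concern.** A woman with a positive fibronectin test and little cervical change and a woman well advanced in dilation enter the same comparison. If their times to delivery differ greatly, a chance excess of dilated women in one arm shortens that arm's time to delivery whatever the drug does. With about 20 per arm, such an excess is not rare. Even without imbalance, a strong predictor left out of the analysis stays in the residual variation and widens the interval.

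Section 10.2 is not simply silent on covariates. It gives a list and a method, and both have weaknesses. The list omits a baseline factor that every randomised woman must have recorded in order to be eligible. It includes treatments that mostly follow randomisation, and adjusting for those can remove or distort part of a treatment effect. The method, looking for differences between the arms, lets observed imbalance choose the covariates. An SAP that follows 10.2 as written would inherit all three.

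**Working it through.** The protocol states no effect size, alpha or power, so there is no figure of its own to reproduce.

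**Inputs from the protocol:** 40 women, 1:1, so about 20 per arm (4.1, 5.5.1); follow-up to EDD + 28 days (section 3), so about 40 deliveries if no woman is lost.

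**Assumptions (no figure in the protocol):** share q of women entering at 3 cm or more, 20-50%; effect of that route on time to delivery, from none to 8-fold; delivery within 7 days, p1 = 70-90% on that route against p0 = 20-30% on the others.

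**1. Chance of imbalance.** P(gap of at least 4 women on one route), 20 per arm:

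| q | Independent binomials (20, q) | Route total fixed at 40q (hypergeometric) |
|---|---|---|
| 0.2 | 0.164 | 0.235 |
| 0.3 | 0.226 | 0.301 |
| 0.4 | 0.258 | 0.333 |
| 0.5 | 0.268 | 0.343 |

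The second column is higher because the fixed totals used are even, so the gap can only be 0, 2, 4 and so on. Together they give 16-34%. A gap of at least 6 women (30 points), with the total fixed, has a chance of 4-11%.

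**2. What an imbalance does to 7-day delivery with no drug effect.** The SD of the difference in route share is √[2q(1−q)/20]. Two SDs are 2 × 0.126 = 0.253 at q = 0.2 and 2 × 0.158 = 0.316 at q = 0.5. Multiplied by p1 − p0:
- smallest: 0.253 × (0.70 − 0.30) = 0.10
- largest: 0.316 × (0.90 − 0.20) = 0.22

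This is a shift of 10-22 percentage points.

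**3. Variance explained by route.** R² = q(1−q)(p1−p0)² / [m(1−m)], with m = q·p1 + (1−q)·p0.
- q = 0.2, 70% v 30%: m = 0.38; 0.16 × 0.16 / (0.38 × 0.62) = 0.11
- q = 0.5, 90% v 20%: m = 0.55; 0.25 × 0.49 / (0.55 × 0.45) = 0.49

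**4. Precision of a log time ratio.** Simulation with 6,000 runs per setting, residual SD of log time 1.2, true treatment effect 0.5 on the log scale, q = 0.2-0.5:

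| Difference in time between routes | Variance, adjusted ÷ unadjusted |
|---|---|
| none | 1.02-1.03 |
| 2-fold | 0.95-0.97 |
| 4-fold | 0.79-0.85 |
| 8-fold | 0.59-0.68 |

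At q = 0.3 and 4-fold, the standard error falls from 0.434 to 0.388. Bias of the unadjusted estimate was 0.01 or less throughout.

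**5. Log-rank test.** Simulation with exponential times, no censoring, treatment hazard ratio 0.5, two-sided 5%:
- Route hazard ratio 4-8: power 29-47% unstratified, about 52% stratified.
- Route hazard ratio 2: roughly unchanged.
- Route not prognostic: stratifying loses 3-4 points.
- Type I error: 5-6% either way.

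**6. The limit set by size alone.** With 40 deliveries, SE(log HR) = 2/√40 = 0.316, so the 95% interval runs a factor of exp(1.96 × 0.316) = 1.86 either way. Schoenfeld power is 59% at HR 0.5, 37% at 0.6 and 20% at 0.7.

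**The case against.** The strongest reply is that covariate choice belongs in the SAP, which is not shown and which section 10.2 requires before unblinding. The sentence about comparing the arms directly spans adherence, adverse events and acceptability as well as time to delivery, so it cannot be naming a model. A reader might infer that the protocol commits to an unadjusted analysis; it does not say so. This stands, and silence on covariates alone would be no finding. What survives is that 10.2 does name a list and a way of choosing from it, and both need correcting.

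A reader might also infer that the protocol itself declares the routes to differ in risk, because section 3 says that "hence preterm birth (with associated neonatal death) is more likely to occur in PIPIN". That sentence compares PIPIN women, all test-confirmed, with the clinically suspected women of an earlier trial. It does not compare the three routes with one another. A strong route effect is clinically plausible but undocumented, and every figure that depends on it is an assumption.

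Two further points stand. Recruitment is primary, no power is claimed, and the small sample limits the estimate more than the omission of route does, unless route effects are very large. And because one test suffices and a woman may meet more than one criterion, dilation or cervical length may be unrecorded for some. The covariate must therefore be the criterion recorded as met, not a full set of cervical measurements.

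**Conclusion.** The point holds as an improvement in precision and prespecification. It does not show that the planned comparison is wrong: an unadjusted comparison is unbiased over repeated randomisation, its type I error is about the nominal level, and its interval already allows for chance imbalance. It would go too far to say that the estimate will be blurred. It may be, by an amount that depends on an unknown route effect.

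The part that needs least assumption is the chance of a gap of at least 4 women on one route, roughly 16-34% for a share of 20-50%. The gain from adjustment rests on assumed effects: a 3-5% fall in variance at a 2-fold difference in time, 15-21% at 4-fold and 32-41% at 8-fold, against a rise of 2-3% if route does not matter. The possible loss is small and bounded, and the possible gain is material. That justifies the change, although time to delivery is only one secondary input to the decision on a larger trial.

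**What to change.** In section 10.2 and the SAP, before unblinding:

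1. Specify that the time-to-delivery comparison is adjusted for, or stratified by, the entry criterion recorded as met before randomisation, at two levels: dilation of 3 cm or more, versus other. State how a woman who meets several criteria is classed, and that a woman with no recorded dilation counts as other.
2. Apply this whether or not the arms look balanced. Do not select covariates from observed differences between the arms.
3. Do not use treatments given after randomisation as confounders; describe them by arm instead.
4. Show entry criterion by arm in the baseline table.
5. Report the unadjusted result alongside as a sensitivity analysis.

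The cost is wording. The tests are done at screening and eligibility is confirmed in the medical records (section 5.3). Because the screening log is anonymised, the criterion should be taken from the eligibility record so that it can be linked to the woman's outcome. The statistical price is one degree of freedom: about 2-3% in variance, or 3-4 points of power with a stratified test, if route proves not to be prognostic.
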